### A3a. Financial Conflict of Interest

Does any member of study personnel (Investigator (including investigator's spouse and/or dependent children)) that are involved in the design, conduct, or reporting of the research have a Significant Financial Interest (SFI) that would reasonably appear to be affected by the research for which funding is sought and/or associated with an entity/business that would reasonably appear to be affected by the research?

No

#### **A5. Funding Source:**

Organization: VA CENTRAL OFFICE, RR&D

#### **A6a. Institution(s) where work will be performed:**

Michael E. DeBakey Veterans Affairs Medical Center

#### **A6b. Research conducted outside of the United States:**

Country:  
Facility/Institution:  
Contact/Investigator:  
Phone Number:

If documentation of assurances has not been sent to the Office of Research, please explain:

#### **A7. Research Category:**

#### **A8. Therapeutic Intent**

Does this trial have therapeutic intent?

No

#### **A9. ClinicalTrials.gov Registration**

Does this protocol/trial require registration on ClinicalTrials.gov due to it: meeting the definition of an Applicable Clinical Trial, being required under the terms and conditions of an award, or being proposed to be published in ICMJE journals?

No, this clinical is not a clinical trial, or does not meet the definition of an Applicable Clinical Trial, or does not need to be registered under the terms and conditions of an award, or is not a clinical trial with results intended to be reported in a journal belonging to the ICMJE. Registration is not required.

### **Section B: Exempt Request**

#### **B. Exempt From IRB Review**

Not Applicable

## **Section C: Background Information**

Veterans with stroke often experience comorbid psychological distress (i.e., depression and anxiety). A recent meta-analysis and systematic review indicates depression is present in 33%, and anxiety is present in 24%, of patients with recent stroke. Untreated or poorly managed psychological distress decreases stroke outcomes for physical functioning (PF), social role functioning (SRF) and quality of life (QoL). PF is often characterized as engagement in activities of daily living (i.e. bathing and grooming) whereas SRF refers to participation in valued social roles, including employee, student, family member, friend, teammate, etc. Impairments in PF and SRF are associated with poor QoL poststroke.

Stroke self-management treatment can improve disability, confidence in recovery, and QoL. Veterans with comorbid stroke and psychological distress have suboptimal outcomes. They are less adherent to PF and physical activity self-management behaviors that promote mobility and experience social isolation; limit interactions with family, friends and community members; and disconnect from social networks. Few self-management treatments address or treat comorbid psychological distress. Enhanced behavioral self-management programs addressing disease-specific self-management and psychological distress have evidenced positive physical, social and QoL outcomes in Veterans with similar neurological conditions. There has yet to be such a treatment for Veterans with stroke and psychological distress. The Co-I, [name], developed the Self-management TO Prevent Stroke using Video teleconferencing (VSTOP-II) intervention that decreases behaviors that are risk factors for stroke and improves stroke health outcomes. The PI, [name], developed a cognitive-behavioral treatment that targets healthy eating and physical activity health behaviors and psychological distress management, Enhancing Psychological Distress Coping (EPiC), which demonstrated improvements in psychological distress and QoL. The 2 programs will be combined to develop a single, behavioral stroke self-management treatment that addresses both stroke risk reduction and psychological distress. The intervention is intended to help Veterans practice health behaviors that reduce risk of a second stroke and is titled "I'm Whole".

## **Section D: Purpose and Objectives**

The overall goal of this study is to develop, refine, and pilot the I'm Whole treatment for Veterans with stroke and comorbid psychological distress. This project will also gather preliminary data on the effects of I'm Whole on QoL, PF (activities of daily living and physical activity), SRF, psychological distress and satisfaction with I'm Whole.

## **Section E: Protocol Risks/Subjects**

### **E1. Risk Category**

Category 1: Research not involving greater than minimum risk.

### **E2. Subjects**

Gender:

Both

Age:

Adult (18-64 yrs)

Ethnicity:

All Ethnicities

Primary Language:

English

Groups to be recruited will include:

Asymptomatic patients with chronic conditions, healthy

Which if any of the following vulnerable populations will be recruited as subjects?

Mentally ill

Vulnerable populations require special protections. How will you obtain informed consent, protect subject confidentiality, and prevent undue coercion?

We will recruit male and female Veterans with mild to moderate symptoms of anxiety and depression. Participants who have poorly controlled mental illness that prevent capacity to provide consent will be excluded from the study. Participants who are unable to provide informed consent or who demonstrate cognitive limitations as evidenced by a score of 3> on a cognitive screen will be excluded from the study. We will use the teach back method of ensuring the Veteran understands the purpose, procedures, benefits and risks of participation of the study to ensure they understand, are able to provide proper consent and to prevent any coercion. Veterans who are unable to successfully repeat back the study information will be excluded. We will also consent individuals after they have discharged from the hospital and have been back in their home setting to prevent obtaining consent from anyone under duress associated with an acute care setting.

### **E3. Pregnant woman/fetus**

Will pregnant women and/or fetuses (as described in 45 CFR 46 Subpart B) be enrolled in the research?

No

### **E4. Neonates**

Will neonates of uncertain viability or nonviable neonates (as described in 45 CFR 46 Subpart B) be enrolled in the research?

No

### **E5. Children**

Will children be enrolled in the research?

No

## **Section F: Design/Procedure**

### **F1. Design**

Select one category that most adequately describes your research:

c) Pilot

Discuss the research design including but not limited to such issues as: probability of group assignment, potential for subject to be randomized to placebo group, use of control subjects, etc.

IM Whole is a 6 session behavioral treatment that addresses psychological distress and stroke self-management behaviors that will be delivered via VT in the home. The treatment will be delivered weekly over 6 weeks. One module will be provided each session. The sessions will last approximately 30-45 minutes. The first module will combine the VSTOP-II stroke self-management education regarding stroke risk factors and EPIC psychoeducation on how comorbid psychological distress can create barriers to engaging in stroke self-management behaviors. Clinicians will work with each Veteran to establish individualized plans for psychological distress management and strategies for practicing tailored PF, physical activity and SRF behaviors in line with the Veteran's values. Progress towards the Veteran's tailored PF, physical activity and SRF behaviors will be reviewed, and psychological distress barriers will be discussed in future modules. Modules 2-5 will be electives that provide cognitive behavioral treatment (CBT) based behavioral activation, social-support, cognitive-restructuring, thought-stopping, deep-breathing, and problem-solving skills for improving psychological distress-related barriers to practicing established PF, physical activity and SRF behaviors. Module 6 consists of a relapse prevention plan for continued management of psychological distress. Homework and tracking logs will be provided at the end of each session. The Co-I, [name], will provide feedback during the development and refinement stages regarding creating tailored PF and physical activity strategies for participants. The Co-I, [name], will provide feedback in the development and refinement stages regarding client-centered strategies for reintegrating into family and community roles and activities poststroke. A clinician manual and patient workbook will be developed.

In phase I: The PI will work with the study team to combine the EPIC and VSTOP treatments into one cohesive treatment called IM WHOLE. No Veterans will be involved in this phase.

In Phase II: The PI will pilot IM Whole by treating 5 Veterans suffering from stroke and comorbid psychological distress. Five Veterans with stroke and comorbid psychological distress will be recruited from the stroke acute care unit, rehabilitation unit, and outpatient stroke follow-up clinic. Qualitative interviews asking the Veterans opinion regarding the treatment content and delivery method will be administered at the end of the final session.

In phase III: Interested Veterans will be randomized to IM Whole (n=15) or usual care plus education (UC+E) (n=15), respectively. Veterans in the UC+E group will receive standard acute care, rehabilitation unit or

outpatient follow-up clinic stroke treatment provided at the MEDVAMC. The standard of care for these patients consists of appointments in the outpatient stroke follow-up clinic, medication management for comorbid chronic diseases, and general physical rehabilitation exercises. To account for additional treatment contact provided to participants in I'm Whole, UC+E will also receive 6 brief telephone calls with information regarding unrelated health topics (e.g., breast, colon, rectal, esophageal, skin and testicular cancer treatment and prevention). We will track the number of patients screened, number and percent of patients eligible, number randomized, number and percent completing treatments, and number and percent completing subsequent follow-up assessments following treatment completion. Veterans in I'm Whole will complete the same qualitative interviews described in phase II.

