In Phase II: The PI will pilot I'm Whole by treating 5 Veterans suffering from stroke and comorbid psychological distress. Five Veterans with stroke and comorbid psychological distress will be recruited from the stroke acute care unit, rehabilitation unit, and outpatient stroke follow-up clinic. The participants will receive each of the I'm Whole sessions using VT in the home. Sessions will be delivered weekly over 6 weeks. Clinicians will work with the Veteran to establish goals in the first session that will be reviewed through the remaining sessions. Qualitative interviews asking the Veterans opinion regarding the treatment content and delivery method will be administered at the end of the final session.

The barriers to receiving the intervention via VT and acceptability of the intervention content and procedures will be assessed informally after each session, and responses will be reviewed at weekly team meetings to address any unanticipated results and make needed immediate changes to the intervention. A semi-structured interview will occur with each Veteran post-treatment, conducted by the RA trained by Co-I [name], an expert in qualitative methods. Interviews will occur by phone and include open-ended questions regarding recruitment; engagement and retention strategies; assessment procedures; participant burden; redundancy and length and frequency of treatment; effectiveness, usefulness of I'm Whole content, and perceived benefits and barriers to receiving the sessions via VT to the Veteran's home. Detailed notes will be taken during interviews, which will also be audio recorded and transcribed for analysis. Rapid analysis is a systematic and rigorous process of condensing qualitative data to quickly identify key findings to inform study progress (i.e., refine and modify I'm Whole content, delivery methods and treatment procedures). The information from the transcribed notes and feedback received in weekly meetings will be used to modify the IM WHOLE treatment.

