Phase II and Phase III: Treatment Procedures and Development-- Sessions will be conducted by 1 clinician with master's-level training in health education, counseling or social work and expertise in CBT, psychological distress treatment, and/or chronic disease management. The clinician will conduct the sessions from the MEDVAMC using VA Video Connect VT to the Veterans in their homes. The MEDVAMC frequently uses VT for clinical treatment and research and has established VT programs and equipment that is VHA approved and readily available.

Assessment Procedures. Each participant in phase II and phase III will receive \$20.00 for each assessment they complete (0/6/12 weeks). Assessments will be conducted by an Independent Evaluator (IE). We estimate that each assessment will take about 30 to 40 minutes. If scores on the psychological distress measure worsen (e.g., 20% or more increase), the PI will be notified and participants referred to mental health treatment within the MEDVAMC or the community.

Phase III: This group will consist of the treatment (*I'm Whole* group) and usual care group will receive the standard of care. The standard of care for these patients consists of appointments in the outpatient stroke follow-up clinic, medication management for comorbid chronic diseases, and general physical rehabilitation exercises. To account for additional treatment contact provided to participants in *I'm Whole*, UC+E will also receive 6 brief telephone calls with information regarding unrelated health topics (e.g., breast, colon, rectal, esophageal, skin and testicular cancer treatment and prevention).

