**Distribution Plan:**

Each participant in phase II and phase III will receive 20.00 for each assessment they complete (0/6/12 weeks).

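### In Phase III, only I'm Whole Veterans have an interview covering effectiveness and benefit; it falls beside the post-treatment assessment, and the plan does not put the assessment first

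*Combined protocol and SAP*

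**What the plan says.** **Who is interviewed.** Section F1, on Phase III: "Veterans in I'm Whole will complete the same qualitative interviews described in phase II". No interview is described for the usual care plus education (UC+E) arm, which receives six brief calls on unrelated health topics.

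**When.** The Phase II text that this refers back to appears in both F1 and F2: "Qualitative interviews asking the Veterans opinion regarding the treatment content and delivery method will be administered at the end of the final session". F2 then gives a second description: "A semi-structured interview will occur with each Veteran post-treatment, conducted by the RA". It is held by telephone ("Interviews will occur by phone and include open-ended questions regarding recruitment"), whereas the sessions are by video. This second description gives no day.

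**What is asked.** F2 lists recruitment, engagement and retention, assessment procedures, burden, redundancy, length and frequency of treatment, and then "effectiveness, usefulness of I'm Whole content, and perceived benefits and barriers to receiving the sessions via VT to the Veteran's home".

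**Outcome assessment.** Under Assessment Procedures (F2) and the Distribution Plan (Section L), assessments are at weeks 0, 6 and 12 in both arms. F2 assigns them to an Independent Evaluator. Section G2 analyses baseline, post-treatment and 12 weeks post-treatment, and reports d at the last two. QoL is primary; psychological distress is among the secondary outcomes. Whether the evaluator is masked to arm is neither stated nor denied.

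**The concern.** Participants know which programme they received, and QoL and distress are the kind of outcome that a recent conversation can colour. If treated Veterans have just been asked whether the programme worked and how it helped them, and controls have had no comparable conversation, their next answers may shift for a reason other than the treatment. Such a shift goes directly into the arm difference. Multiple imputation and the completer analysis deal with missing data and would not remove it.

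The plan itself treats unequal contact as something to balance: the UC+E calls exist for that purpose. The interview is an additional contact in one arm, close to a scoring point. Because Section G1 says the study is underpowered for efficacy, the effect sizes are likely to be what is carried forward from Phase III.

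**Working it through.** **1. Where the final session falls.** Six weekly sessions span five intervals: 5 × 7 = 35 days from first to last. The gap between baseline and the first session is not given, so two cases are assumed.
- First session on the baseline day: last session on day 35, and the week-6 assessment (day 42) is 7 days later.
- First session one week after baseline: last session on day 42, the same day as the assessment.

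Section G2 calls this time point post-treatment, so the assessment belongs at or after the last session.

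**2. The two interview descriptions against that assessment.**

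| Description | Timing | Order relative to the post-treatment assessment |
|---|---|---|
| F1 and F2 | End of the final session | Same day, or up to about a week before |
| F2 | Post-treatment, by phone, by the research assistant | Not given; could be either side |

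The two can be read together (a call just after the last session) or apart (a call some days later). Neither puts the assessment first.

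**3. Which estimates are exposed.** The post-treatment d is the one at risk. The last assessment comes well after the interview: 12 − 6 = 6 weeks on the payment schedule, or 12 weeks on G2's label. Any short-lived prompt should have weakened by then.

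**4. Size, as an illustration.** The plan states no figure for reporting bias, no significance level and no SD, so there is nothing to reproduce. Assume a shift of b SD in the I'm Whole arm only; d then changes by b. The standard error of d is approximately √(2/n) with n per arm.
- n = 15, as randomised: √(2/15) = 0.365.
- n = 12, after the 20% loss in G2 (15 × 0.8): √(2/12) = 0.408.

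| Assumed b | Share of SE, n = 15 | Share of SE, n = 12 | Share of an assumed true d of 0.5 |
|---|---|---|---|
| 0.1 | 0.1/0.365 = 27% | 0.1/0.408 = 25% | 20% |
| 0.2 | 0.2/0.365 = 55% | 0.2/0.408 = 49% | 40% |

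With no true effect, a two-sample t test at an assumed two-sided 5% level has 2n − 2 degrees of freedom and noncentrality b√(n/2). Its rejection rate would be 5.8% (b = 0.1) or 8.3% (b = 0.2) at n = 15, and 5.6% or 7.6% at n = 12. This is a simple comparison at one time point, not the planned model. A negative b would lower d by the same amount.

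**The case against.** Several points on the other side stand.

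- **Order.** A reader might infer that the interview definitely precedes the assessment. The documents do not say so. The end-of-session wording makes it likely, but F2's other description leaves the day open, and on a shared day the assessment could come first.
- **Masking.** A reader might infer that the evaluator is unmasked through team meetings, medical-record notes or the interview. None of these is shown. The weekly meetings are described for Phase II, which has one arm. The record notes in F2 document the enrolment visit or the reason for ineligibility and are not said to name the arm. The research assistant, not the evaluator, conducts the interview. What remains is that masking is not stated.
- **Measurement.** A reader might infer that measurement differs by arm. The schedule, evaluator and payment are the same for both. What differs is one extra contact near a scoring point, which is a risk of differential reporting.
- **Direction.** Many interview topics are neutral or critical (burden, redundancy, barriers), so a net shift in favour of I'm Whole cannot be taken for granted. These Veterans have also reviewed their goals with a clinician for six sessions, so one further conversation may add little. The documents do not name the QoL instrument, so self-report is an assumption.
- **Time point.** The hypothesis in G2 is set at 12 weeks post-treatment, where the prompt is weeks old. This is a pilot that its own protocol calls underpowered.

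These limit the claim without removing it. The plan gives a timing rule, the rule applies to one arm, and post-treatment d is a reported result.

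**Conclusion.** The concern holds as an avoidable risk in the post-treatment comparison. An interview given to one arm, with effectiveness and benefit among its topics, is placed beside the post-treatment assessment, and no rule has the outcomes scored first. Its size and direction cannot be derived from the documents; the 0.1 to 0.2 SD range, the d of 0.5 and the 5% level are all assumptions. The conclusion rests on the end-of-final-session wording being followed and on QoL and distress being reported by the Veteran. The 12-weeks-post-treatment comparison is less affected. The silence on masking is a secondary gap in description and does not show that the evaluator knows the arm. The case for acting is that the risk can be removed from the post-treatment assessment at almost no cost.

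**What to change.** 1. In Phase III, hold the interview only after the Independent Evaluator has completed that Veteran's post-treatment assessment.
2. Reconcile the two interview descriptions in F1 and F2 into one, giving interviewer, mode and timing relative to the last session and the assessment.
3. As a secondary clarification, state in Assessment Procedures whether the Independent Evaluator is masked to arm. If so, add a short script asking Veterans not to mention their programme.

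The cost is a scheduling rule, a few sentences and a short script, with the staff already planned. The downside is that the interview may fall a few days after the last session. The reordering protects the post-treatment assessment only, because the last assessment would still follow the interview.

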**Inclusion Criteria:**

Inclusion for Phase II and Phase III: 1) a documented history of stroke and/or transient ischemic attack within the last 30 days, 2) a modified Rankin score of > 3, 3) regular access to a computer or tablet with internet and a camera, 4) ability to give appropriate informed consent, 5) score > 5 on a measure of depression (Patient Health Questionnaire [PHQ-8]) and/or >17 on a measure of anxiety (Generalized Anxiety Disorder-7 [GAD-7]) assessments, 6) ability to ambulate with or without assistance of a cane or walker.

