Phase II and Phase III: Screening and Recruitment Procedures. We will recruit men and women Veteran stroke patients of all races and ethnicities with depression and anxiety symptoms who are being treated in the stroke acute care inpatient unit, rehabilitation unit, or outpatient stroke follow-up clinic at the Michael E. DeBakey VA Medical Center (MEDVAMC). The MEDVAMC treats over 310 Veterans with stroke each year, of which approximately 93 (33%) have comorbid psychological distress. We have successfully recruited Veteran stroke patients in our previous stroke studies. The research assistant (RA) will approach potential participants at bedside in the acute or rehabilitation unit or during the first follow-up visit after admission from the stroke acute care unit. Veterans interested in the study will be screened for eligibility via their electronic medical records (EMR) to see if they meet preliminary study inclusion/exclusion criteria (listed above). Those who meet the eligibility criteria will receive a follow up session, in their home or at the MEDVAMC to be administered the screening measurements listed above. If participants via EMR review or baseline assessments: 1) do not demonstrate or show evidence of a cognitive impairment, as evidenced by a score of >3 on a brief cognitive screener; 2) have a documented diagnosis of psychotic disorder or schizophrenia; 3) score in the severe range for depression, or anxiety (based on PHQ-8 or GAD-7 score of > 20), or have a documented or self-reported hospitalization for psychiatric illness within the past 30 days, they will be invited to participate in the study. They will be provided instructions regarding using VTEL to conduct their sessions, given a *I'm Whole* workbook and scheduled a time for first session with the study clinician. A note will be placed in the electronic medical records (EMR)s documenting the visit. Participants who do not meet the criteria will be immediately notified of their ineligibility. A note will be placed in the EMR documenting why they were not eligible. Their primary care provider will be signed to the note for follow up discussion regarding possible referrals or additional services needed for the Veteran. The Veteran will also be provided a list of community based psychiatric and medical resources.

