## Section G: Sample Size/Data Analysis

### G1. Sample Size

How many subjects (or specimens, or charts) will be used in this study?

Local: 50      Worldwide: 50

Please indicate why you chose the sample size proposed:

Phase I: does not involve participants. We plan to recruit 5 participants for phase II and 30 participants for phase III. To account for a 40% drop out rate the PI evidenced in a prior study using Video telehealth, we will over recruit for phase II and phase III. Recruitment feasibility of approximately 6 subjects per month is based on the number of participants from [name] VSTOP study who also had comorbid psychological distress. The study is underpowered to show clinically meaningful efficacy of *I'm Whole* when compared to usual care.

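### As printed, the modified Rankin criterion conflicts or nearly conflicts with the ambulation criterion, leaves little room for TIA-only Veterans, and is not reflected in the recruitment figures

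*Combined protocol and SAP*

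**What the plan says.** The Inclusion Criteria in F1 form a single list for Phases II and III. No either/or is stated between its six items, so all must hold together. Three of them matter here:

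- Item 1, the index event: "1) a documented history of stroke and/or transient ischemic attack within the last 30 days".
- Item 2, disability: "2) a modified Rankin score of > 3".
- Item 6, mobility: "6) ability to ambulate with or without assistance of a cane or walker".

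E2 enters the recruited group as "Asymptomatic patients with chronic conditions, healthy". Section D describes the aim as to "develop, refine, and pilot the I'm Whole treatment for Veterans with stroke and comorbid psychological distress". It gives no disability level and does not mention TIA.

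On recruitment, F2 says that the centre "treats over 310 Veterans with stroke each year, of which approximately 93 (33%) have comorbid psychological distress". G1 adds: "Recruitment feasibility of approximately 6 subjects per month is based on the number of participants from" an earlier stroke self-management study who also had psychological distress. G1 gives a total of 50 subjects, with 5 planned for Phase II and 30 for Phase III. The Phase III description in F1 says that the study will track how many patients are screened, eligible and randomized.

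**The concern.** Item 2 sets a floor on disability and item 6 sets a floor on mobility. The two pull in opposite directions, and the documents do not say where they are meant to meet. Item 1 then invites Veterans whose only event was transient, which sits poorly with a high disability floor.

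Two things are at stake. The first is consistent application: if staff find that a Veteran can rarely satisfy items 2 and 6 together, they must either turn away nearly everyone or bend one of the items, and different staff may bend different ones. The second is the pilot's feasibility data. The number and percent eligible are among its tracked results. If the eligibility rule is internally inconsistent, those figures partly measure the rule's wording, and they become a poor guide for planning a larger trial. The disability level enrolled also affects how the physical-functioning and physical-activity data can be read.

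**Working it through.** **Step 1. Which grades meet items 2 and 6 together.** The documents define no grades. Assumption, from the scale's ordinary grading: 3 = needs some help but walks without assistance; 4 = unable to walk without assistance; 5 = bedridden. Both the sign in item 2 and the meaning of assistance in grade 4 are varied.

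| Reading of item 2 | Assistance in grade 4 means another person | A cane or walker counts as assistance |
|---|---|---|
| > 3, as printed (grades 4–5) | none | grade 4 only |
| ≥ 3, if the sign was flattened (grades 3–5) | grade 3 only | grades 3 and 4 |

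As printed, the overlap is therefore zero grades or one. Under ≥ 3 it is one or two, and the conflict with item 6 largely disappears.

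**Step 2. TIA.** On every reading in the table a TIA-only Veteran needs a grade of at least 3. A transient event would not ordinarily leave that deficit by itself, so such a Veteran would qualify mainly through disability from another cause. Item 2 does not require the disability to come from the index event, so this is possible but would be uncommon.

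**Step 3. The recruitment pool.** The plan's own figure first: 0.33 × 310 = 102.3, not 93. In fact 93/310 = 30%, and 93/0.33 = 282. This mismatch is a separate arithmetic matter and proves nothing about the criteria; 93 is kept below as the plan's figure.

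Stated accrual: 6 × 12 = 72 a year, and 72/93 = 77% of the pool. At that rate 50 subjects take 50/6 = 8.3 months. Neither the 93 nor the 6 is described as allowing for item 2 or item 6.

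**Step 4. Sensitivity to the unknown share.** Let f be the share of the 93 who meet both items; no value for f appears in the documents. If everyone eligible consents and no other criterion removes anyone:

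months to reach N = 12 × N / (93 × f)

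| Assumed f | Eligible per year | Months to 35 | Months to 50 |
|---|---|---|---|
| 5% | 4.7 | 90 | 129 |
| 10% | 9.3 | 45 | 65 |
| 20% | 18.6 | 23 | 32 |
| 50% | 46.5 | 9 | 13 |
| 77% | 71.6 | 6 | 8 |

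On the 93-a-year pool, the stated accrual needs f of about 77% even under these favourable conditions. The pool figure is for stroke; TIA-only Veterans might add to it, by an amount the documents do not give.

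**The case against.** The strongest reply is that the emptiness comes from the assumptions. The grades are not in the documents, and the result turns on how grade 4 is worded. Item 6 expressly allows a cane or walker, so a reader who takes it to require independent walking goes beyond its text. The sign may also be an artefact: a bare > appears at every threshold in the inclusion and exclusion lists, and an underlined sign or a ≥ could have been flattened when the PDF was read. All of this stands. It is why the conclusion is a conflict or near conflict, with moderate confidence.

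It also stands that naming TIA widens item 1, and that a second item narrowing the first is not in itself a contradiction. The E2 line is an entry under a form heading. The same section describes recruits with mild to moderate anxiety and depression symptoms, so the entry fits poorly whatever the Rankin range and cannot show which range was meant.

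Nor do the criteria contradict the objectives. Section D names no disability level, Section C illustrates physical functioning with basic self-care, and recruitment includes acute and rehabilitation units. Enrolling more disabled Veterans is compatible with that. What can be said is that items 2 and 6 narrow the stated stroke-plus-distress population to a subgroup that the plan does not explain.

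The objection does not remove the problem. As printed, at most one grade meets both items; under ≥ the TIA difficulty remains; and nothing in the exclusion list or in F2 clarifies item 2. Direction is unreliable elsewhere too: E2 prints the cognitive cut-off with the sign after the number and the exclusion list prints it before, so staff cannot safely guess the intent.

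**Conclusion.** The point holds in limited form. As printed, items 2 and 6 share no grade or only grade 4, depending on what assistance means in grade 4. If the sign should be ≥, the conflict with ambulation largely goes, while TIA-only Veterans would still rarely qualify. Both statements rest on the assumed ordinary grading.

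A reader might infer that the criteria select almost nobody. The documents do not support that: they give no Rankin distribution, so f is unknown, and the times in the table illustrate how much depends on it without estimating it. A reader might also infer that the sign was simply reversed. The documents do not settle the intended direction, and this review does not choose one.

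What is established is that the eligibility rule cannot be applied consistently as written, that the recruitment figures show no allowance for items 2 and 6, and that the eligible counts would partly reflect the drafting. The accrual comparison has its own limit: the earlier study's entry criteria are not described, so some filtering may be implicit in the 6 a month. Confidence is moderate.

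**What to change.** Before Phase II opens:

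1. Check the sign in item 2 against the signed protocol, to rule a text-reading artefact in or out.
2. Reconcile items 1, 2 and 6. State one Rankin range, with direction and endpoint, that can hold together with the ambulation item. Keep TIA in item 1 only if that range can admit it. The investigators must decide which disability range is intended; no threshold is proposed here.
3. Make the group entry in E2 consistent with the reconciled list.
4. Recheck the 93 a year in F2 and the 6 a month in G1 against the reconciled criteria, and state the share of the pool assumed to meet them.

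The cost is one protocol amendment and a short recheck of the recruitment figures. The amendment itself adds no participants and no procedures.
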